## 9.4 Additional Analyses

### 9.4.1 Alternative specifications for efficacy and toxicity models

We have specified a form for  $\pi_E$  that models efficacy curves for the previously-treated and not previously-treated groups that are piece-wise parallel on the log-odds scale, as used in scenario 7 of the simulation study and depicted graphically in Table 7. This specification could be invalidated by the presence of a strong interaction effect between PD-L1 and pre-treatment statuses on the odds of efficacy. This is the focus of simulation scenarios 8-12, where the BEBOP design copes admirably well. Similarly, we have modelled toxicity as constant in probability across the cohorts. If either of these assumptions seems to be invalidated by the outcomes we collect, we would consider a secondary analysis with alternative specifications for the efficacy and / or toxicity models given in Section 9.2.1. The chosen form for the alternative models would reflect the nature of the outcomes observed and the inferences of such would be compared to those of the primary analysis, specifically with regard to differences in the model structures.

---

#### 9.4.2 Alternative analysis of the efficacy outcomes

Wason and Seaman [7] present the augmented-binary (Aug-Bin) method for analysing change in tumour size as a continuous variable and show their method to be a more efficient than analysing the dichotomised response variable via RECIST in a setting with two post-baseline assessments of disease. Wason and Lin are currently researching the method in a “best response” scenario using an arbitrary number of disease assessments, as used in PePS2. If their method is published and implemented in R, we plan to use it for a secondary analysis of the efficacy outcomes of PePS2. The applicability of their method in PePS2 is challenged by our cohort structure. One feasible approach is to implement their method in each cohort singly. However, we saw the cost of ignoring the cohort structure via the beta-binomial models in our simulation study. An alternative approach is to implement their method separately in the three PD-L1 groups. This would be permissible if the effect of pre-treatment on efficacy is small. A third approach is to implement their method on the whole PePS2 population. Both BEBOP and the Aug-Bin method aim to increase the efficiency of phase II clinical trials. It may be illuminating to compare the different ways in which Aug-Bin can be applied in a biomarker-driven phase II trial, and how the efficiency compares to that of BEBOP, an alternative that retains dichotomised outcomes yet incorporates predictive baseline information. This planned analysis is completely separate to the primary analysis, will be taken for academic interest, and is contingent on the extended Aug-Bin method being published and programmed in R.

#### 9.4.3 Relationship of PD-L1 proportion score with primary outcomes

Garon et al [1] presented and validated the PD-L1 categorisation used in Table 1. As much is feasible with our sample size, we will analyse the effect of PD-L1 score on our primary outcomes. Some questions that will motivate exploratory analysis are:

1. Are the Garon PD-L1 categories valid in our PS2 patient population?
2. Are alternative categories suggested by our data?
3. Can the continuous PD-L1 score (rather than its dichotomisation) be used to model probability of efficacy?

The answer to 1) will be revealed as part of planned primary analysis. An answer to 2) using dichotomised outcomes could be revealed by using classification trees and n-fold cross-validation. Further research would be needed to answer 2) from the perspective of survival. Question 3 can be answered using plots and logistic models. For instance, simple plots of PD-L1 score vs best response / PFS / OS; or more complex joint-models of tumour size and survival, adjusted for PD-L1 score could be revealing.

Once again, this analysis is exploratory and supplementary to the planned primary analysis.

### 9.5 Subgroup Analysis

The primary analysis of the co-primary outcomes adjusts for categorical variables reflecting PD-L1 score and previous treatment, as demonstrated in Table 2.

Summaries of all outcomes may be calculated and presented in the subgroups defined by the stratifying variables listed in Table 2. Analysis methods will mirror those of the main population.

## 10. RULES OF INFERENCE

On occasion, data required in the analysis will be missing. If data are not available and cannot be obtained by query, the following rules of inference will be used to maximise data coverage.

### 10.1 Previous Cancer Treatment

In the vwPreviousCancerTreatment view, if the CancerTrtBoolID field is missing and TypeID\_txt is provided, the patient will be inferred to have received previous cancer treatment. This would be used

---

to infer that previous cancer therapy has been received when a specific therapy is identified but confirmation that the patient received previous cancer treatment is omitted.

## 10.2 Cycle number

Sometimes the numerical cycle number is not specified but it may be inferable from the time-point label (e.g. 'Treatment cycle 6').

## 10.3 Sum of target lesion diameters and response with respect to target lesions

On the form detailing the RECIST assessments by CT scan, there are fields to report the response category with respect to the target lesions (RTL), and the sum of target lesion longest diameters (STLLD). When RTL is reported and STLLD is not, the missing value may be imputed to be the value closest to baseline consistent with the response categorisation. Effectively, this means that STLLD will be imputed to be: 0 when RTL = CR; 0.7 \* baseline, when RTL = PR; 1.2 \* baseline when RTL = PD. Likewise, RTL may be imputed when it is missing and STLLD is reported by comparing STLLD to baseline. In any given analysis, the number of imputed values will be reported and justified. If we use this method, we envisage it will be to maximise information on supporting graphical analyses like waterfall and spider plots.

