### Response Criteria

#### A. Evaluation of Target Lesions

Response Category	Description
Complete Response (CR)	Disappearance of all target lesions
Partial Response (PR)	At least a 30% decrease in the sum of the LD of target lesions, taking as reference the baseline sum LD
Progressive Disease (PD)	At least a 20% increase in the sum of the LD of target lesions, taking as reference the smallest sum LD recorded since the treatment started or the appearance of one or more new lesions. In addition to this, the sum must also demonstrate an absolute increase of at least 5 mm. The appearance of one or more lesion is also considered progression.
Stable Disease (SD)	Neither sufficient shrinkage to qualify for PR nor sufficient increase to qualify for PD, taking as reference the smallest sum LD since the treatment started

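### SAP 10.3 fills in missing target-lesion responses and sums from baseline alone, whereas Protocol Appendix 2 measures progression by size from the smallest sum on study with a 5 mm minimum; the likely effect is small

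*SAP*

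**What the plan says.** SAP section 10 sets rules for gaps that a query has not closed: "On occasion, data required in the analysis will be missing". Section 10.3 covers two fields on the RECIST form, in two directions.

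- **Response reported, sum missing:** "the missing value may be imputed to be the value closest to baseline consistent with the response categorisation". The SAP spells this out as 0 for CR, 0.7 × baseline for PR and 1.2 × baseline for PD. It lists no value for SD.
- **Sum reported, response missing:** "Likewise, RTL may be imputed when it is missing and STLLD is reported by comparing STLLD to baseline". No cut-offs are given.

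On scope, 10.3 adds "In any given analysis, the number of imputed values will be reported and justified" and says that, if the method is used, "we envisage it will be to maximise information on supporting graphical analyses like waterfall and spider plots".

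Protocol Appendix 2, Response Criteria A, refers PR to the baseline sum. PD is an increase of at least 20%, "taking as reference the smallest sum LD recorded since the treatment started or the appearance of one or more new lesions", and "the sum must also demonstrate an absolute increase of at least 5 mm". It continues: "The appearance of one or more lesion is also considered progression". SD is also judged against the smallest sum. SAP 9.1.1 (DCB) says that tumour burden is assessed by RECIST 1.1 in line with the protocol.

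**The concern.** Neither the smallest sum on study nor the 5 mm minimum appears in 10.3. Once a tumour has shrunk, a comparison with baseline uses the wrong reference for progression. Regrowth that Appendix 2 calls PD can then be coded SD or PR. For small tumours the missing 5 mm condition can act the other way. The fixed value for a missing PD sum has the same fault.

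The stake would be larger if imputed values fed outcomes. DCB requires no earlier PD, and TTP, PFS, DOR and DSD all depend on when PD occurs. Section 10.3 states an expectation of graphical use, not a limit. The sentence in SAP 9.2.2.1 that rules out imputing outcomes applies only to the covariate method described there.

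**Working it through.** The documents give no tumour sizes, so all sums below are illustrative, in mm. Write b for the baseline sum, n for the smallest sum so far (baseline included) and s for the current sum.

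**1. The SAP's own multipliers.** From Appendix 2, PR begins at 1 − 0.30 = 0.7 × b, which always agrees with 10.3. PD begins at 1 + 0.20 = 1.2 × b only if n = b and 20% of b is at least 5 mm, that is b ≥ 5/0.20 = 25 mm.

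**2. Appendix 2 threshold for PD by size.** T = max(1.2n, n + 5).

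**3. Response missing, sum reported.** Whatever cut-offs are used, a comparison with baseline cannot turn a sum below baseline into PD. The last column takes 0.7b and 1.2b as cut-offs, which is our reading of 10.3.

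| b | n | s | change from n | T | Appendix 2 | s/b | against baseline |
|---|---|---|---|---|---|---|---|
| 100 | 55 | 70 | +27%, +15 mm | 66 | PD | 0.70 | PR |
| 100 | 80 | 100 | +25%, +20 mm | 96 | PD | 1.00 | SD |
| 20 | 11 | 18 | +64%, +7 mm | 16 | PD | 0.90 | SD |
| 20 | 20 | 24 | +20%, +4 mm | 25 | SD | 1.20 | PD |

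With those cut-offs and b = 100, PD by size is missed for sums from 66 to below 120 (n = 55), 96 to below 120 (n = 80) and 108 to below 120 (n = 90). The opposite error, in the last row, needs a baseline below 25 mm; the plain case is where baseline is still the smallest sum.

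**4. Sum missing, response reported.** The value closest to baseline that is still PD by size is max(b, T). At b = 100:

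- n of 83.3 or less (1.2n ≤ 100): closest value 100, SAP value 120, difference 20
- n = 85: closest value 102, difference 18
- n = 90: closest value 108, difference 12
- n = 100: closest value 120, no difference

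For a reported PR, the SAP value of 70 itself meets PD by size when 1.2n ≤ 70, so n ≤ 58.3. For SD, where no value is listed, baseline would be the natural choice, but it meets PD by size when n ≤ 83.3. If the RTL field can record PD because of a new lesion, no sum is implied at all. Appendix 2 table A lists new lesions under target-lesion PD, while table D gives them a separate column.

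**5. Where the values could go.** SAP 9.2.2.2 defines the spider plot as the sum over time, so an imputed sum can appear there. Waterfall bars show best change and do not move where the smallest sum is recorded. The swimmer plot shows responses and progressions. An imputed RTL reaches it, or DCB, OR, TTP, PFS, DOR or DSD, only if someone derives overall response from that RTL together with non-target and new-lesion status (Appendix 2 table D). For DCB with scans on schedule, that means shrinkage at week 9, regrowth at week 18 with the response blank and the query failed, no new lesion and no non-target PD.

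**The case against.** The best defence is that 10.3 imputes two form fields and never claims to impute overall response. Best response, TTP and PFS rest on recorded assessments (SAP 9.1.2), DCB on RECIST 1.1 as applied under the protocol (SAP 9.1.1), and an undetermined DCB counts as failure (SAP 9.1.1 and 9.2.2). The rule is optional, comes after a query, and its use must be counted and justified. Appendix 2 also says in general terms that the baseline sum is the reference for objective response, which may explain the wording of 10.3.

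Most of this stands, and it limits the reach of the point. A reader might infer that 10.3 will bias DCB or PFS, or that miscoded progressions will show in the swimmer plot. The documents do not support that, because no passage says overall response is built from an imputed RTL. They do not rule it out either, and they do not say whether 10.3 is applied before the default to failure.

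A reader might also take the differences of 12 to 20 mm as error against the patient's tumour. They are not: the true sum is unknown and could be 120 mm or more. They measure only how far 10.3 departs from its own principle.

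The defence does not remove the conflict. The general sentence about baseline does not override the specific PD row, and the spider plot lies within the use that 10.3 expects.

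**Conclusion.** The point holds as a minor one. As written, 10.3 gives classifications that contradict Appendix 2. It misses PD by size after shrinkage and, if 1.2 × baseline is the cut-off, can declare PD too early when baseline is below 25 mm. Its fixed PD sum breaks its own principle once the smallest sum is below baseline, and its PR sum can itself meet PD after a deep response.

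The missed-progression result needs no assumed cut-offs for sums below baseline; the bands and the opposite error do. The new-lesion remark depends on how the RTL field is completed, which the documents do not show. How often one field is blank while the other is filled is not given. Given the safeguards, the likely effect is small, and any effect on endpoints is conditional.

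**What to change.** Amend SAP 10.3 as follows, with n the smallest known sum so far, baseline included.

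1. **Scope.** State that imputed RTL or STLLD values are used only in supporting graphics and never to derive DCB, OR, TTP, PFS, DOR or DSD.
2. **Response missing.** Code PD if the sum is at least 1.2n and at least n + 5 mm. This stands even if an earlier sum is missing, because a lower n only lowers the threshold. Otherwise code CR or PR against baseline, else SD. If the result is not PD and an earlier sum is missing, leave the response missing.
3. **Sum missing.** For PD by size use max(baseline, 1.2n, n + 5 mm). For PR use 0.7 × baseline and for SD use baseline, in each case only if that value does not itself meet PD by size; otherwise leave the sum missing. Also leave it missing when PD is by new lesion or the form does not show which kind of PD it is.

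The cost is a short SAP edit and a few lines of code. No new data are needed, since the serial sums are on the RECIST form. The downside is possibly a few more blank points on the plots.

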## 11. STATISTICAL SOFTWARE

We have implementations of our PePS2 BEBOP design written in Python and Stan [3]. The Python implementation solves posterior integrals directly using Monte Carlo integration. Stan is a Bayesian programming language. The Stan implementation uses No U-Turn Sampling to sample elements from the posterior distribution. The two methods agree on the six-parameter model presented. The Python method cannot realistically be used on problems with more than six parameters because of the non-linear increase in difficulty of directly calculating integrals of higher dimension (the *curse of dimensionality*). The Stan method was developed with the prospect of analysing models with more than six parameters.

## 12. STORAGE AND ARCHIVING

Snapshots of the data used in interim analyses for TSC meetings will be stored beneath:

T:\Trials Work\EDD\PePS2\PePS2Analysis\TSC\

A snapshot of the data used for publications will be stored beneath:

T:\Trials Work\EDD\PePS2\PePS2Analysis\Publications\

A snapshot of the data used in the final analysis will be stored beneath:

T:\Trials Work\EDD\PePS2\PePS2Analysis\EndOfTrial\

## 14. APPENDIX

**Table 7 - Curves showing PD-L1 cohort vs log-odds of efficacy, for previously-treated and –untreated patients, in simulation scenarios.**
